5.1 Preparation Phase

- Participants will rest for 30 minutes after signing consent to stabilize vital signs;

- Baseline heart rate will be recorded. Laser protective glasses and ECG monitoring devices will be worn;
- The operator will preset the laser device parameters.

5.2 Experimental Procedure

- Three sites in the maxillary anterior vestibular groove with intervals >20 mm will be selected;
- Interventions will be applied in random order (laser irradiation and subsequent drug application);
- Penetration tests will be performed at 10, 20, 30, 40, and 50 minutes after treatment. Penetration depth, VAS score, and heart rate will be recorded at the moments of "sensation" and "pain";
- Adverse reactions (redness, pain, bruising, etc.) will be assessed immediately after the procedure and at 24-hour follow-up.

6. Statistical Analysis

- Data will be analyzed using SPSS 27.0. Normally distributed continuous variables will be expressed as mean \pm standard deviation ($\bar{x} \pm s$);
- Repeated measures ANOVA will be used to compare differences across time points and groups. If the sphericity assumption is violated, multivariate tests (Roy's Max Root) will be applied;
- Pairwise comparisons will be performed using Bonferroni correction with significance level $\alpha = 0.05$;
- A p-value < 0.05 will be considered statistically significant

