Study Protocol and Statistical Analysis Plan

Official title: The effect of Er,Cr:YSGG laser-assisted topical anesthetic on oral mucosal anesthesia

NCT number: NCT07169032

Document date: 12/25/2023

This study is a randomized controlled clinical trial with a single-blind design. The protocol has been approved by the Medical Ethics Review Committee of Jinan University (Approval No.: JNUKY-2023-0149). All participants will provide written informed consent before the study begins.

1. Study Participants

The study will be conducted in an outpatient setting, with a total of 20 participants (10 males and 10 females). Participants will be recruited through online advertisements and from among outpatient clinic visitors. All participants will receive free oral health examinations and related treatments as compensation.

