1.2 Exclusion Criteria

- Severe dental anxiety;
- Allergy to local anesthetics;
- Presence of oral mucosal lesions;
- History of cardiovascular disease;
- History of diabetes;
- Pregnant or lactating women;
- History of severe psychiatric disorders;
- Hearing or speech impairments.

2. Group Allocation

This is a single-blind randomized controlled trial. After providing informed consent, participants will be stratified by gender. Three sites in the mandibular anterior

vestibular groove will be selected and randomly assigned to one of the following three interventions:

- Experimental group: Irradiation with Er,Cr:YSGG water laser (wavelength 2780 nm, power 1.0 W) for 1 minute, followed by application of 2% lidocaine gel;
- Control group: Irradiation with placebo laser (0.1 W) for 1 minute, followed by application of 2% lidocaine gel;
- Blank group: Irradiation with placebo laser (0.1 W) for 1 minute, followed by application of petroleum jelly.

All procedures will be performed by the same operator and assistant. Participants will be blinded to group assignment.

3. Materials and Equipment

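### Site position and application order are randomised within each participant, but no balancing of either is described and the Section 6 model has no term for them, which can cost precision

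*Combined protocol and SAP*

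**What the plan says.** - Size (Section 1): the trial runs "with a total of 20 participants (10 males and 10 females". No effect size, standard deviation or power accompanies this number.
- Allocation (Section 2): "participants will be stratified by gender", and three sites in the "vestibular groove will be selected and randomly assigned to one of the following three interventions". No list method, block size or Latin square is given.
- Order (Section 5.2): "Interventions will be applied in random order (laser irradiation and subsequent drug application". Again no method is given.
- Sites (Section 5.2): "Three sites in the maxillary anterior vestibular groove with intervals >20 mm will be selected". Section 2 places the three sites in the mandibular groove instead.
- Testing (Section 5.2): "Penetration tests will be performed at 10, 20, 30, 40, and 50 minutes after treatment", so there are five tests at each of three sites, or 15 per participant.
- Analysis (Section 6): "Repeated measures ANOVA will be used to compare differences across time points and groups". The plan adds "Pairwise comparisons will be performed using Bonferroni correction with significance level" 0.05. It names no term for site position, application order or gender.

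**The concern.** Every participant supplies an Experimental, a Control and a Blank site. Gender is the same for all three, so it drops out of the main intervention contrasts, and stratifying by it does nothing to balance them. Two things do differ between interventions within a mouth: which site each one occupied, and when in the sequence it was applied. Three sites spaced along one anterior groove would most naturally be one central and two lateral, though the plan does not say so. Depth, VAS and heart rate are all primary outcomes. The last two are whole-person responses that could drift over 15 needle tests.

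A position or order effect that is neither balanced nor modelled does two things. It adds to the error variance of every contrast, and in the one trial that is run a chance imbalance shifts the estimate. A model with only time and group cannot remove that shift. With 20 participants, no stated power and a Bonferroni-adjusted threshold, precision is worth protecting.

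**Working it through.** The plan gives no calculation for its sample size, so there is no figure to reproduce.

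**Inputs from the documents.** N = 20, 10 per gender (Section 1). Three sites and three interventions per participant (Section 2). Alpha 0.05 with Bonferroni (Section 6), hence 0.05/3 = 0.0167 for each of three pairwise contrasts, taken as two-sided.

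**Assumptions.** The middle site differs from both lateral sites by d, in units of the total SD. Two sites in one mouth correlate at rho, set to 0.5 or 0.7. There is one value per site. The comparator is simple randomisation with no position or order term.

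**Step 1. Chance imbalance.** For each participant, the middle site holds Experimental (+1), Control (−1) or Blank (0), each with probability 1/3. Summing 20 such steps exactly gives P(difference of 4 or more) = 0.340 and P(6 or more) = 0.132. A difference of 4 shifts the Experimental–Control estimate by 4/20 × d = 0.2d, which is 0.1 SD when d = 0.5.

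**Step 2. Variance of the contrast.** The position part of each participant's difference is +d, 0 or −d with probability 1/3 each, so its variance is 2d²/3. Then:

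- unbalanced and unadjusted: [2(1 − rho) + 2d²/3]/20
- position removed: 2(1 − rho)/20

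| d | rho | Unadjusted | Removed | Cut |
|---|---|---|---|---|
| 0.25 | 0.5 | 0.0521 | 0.0500 | 4% |
| 0.5 | 0.5 | 0.0583 | 0.0500 | 14% |
| 0.5 | 0.7 | 0.0383 | 0.0300 | 22% |
| 1 | 0.5 | 0.0833 | 0.0500 | 40% |

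These are ceilings. They ignore the small remaining imbalance and the degrees of freedom spent. An order effect of the same shape and size would add the same amount again.

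**Step 3. Degrees of freedom.** 60 site values − 20 participants − 2 intervention terms = 38. Position and order take 2 each, leaving 34.

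**Step 4. Interval width.** Simulated (4,000 trials per cell), as the change in mean width of the Experimental–Control interval against the comparator. No order effect was simulated, so the order term is pure cost here.

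| d | rho | Near-balance + both terms | Near-balance, no terms | No balance, position term | No balance, both terms |
|---|---|---|---|---|---|
| 0 | 0.5 | +1% | 0% | +3% | +6% |
| 0.25 | 0.5 | −1% | 0% | +1% | +4% |
| 0.5 | 0.5 | −6% | 0% to +1% | −4% | −2% |
| 0.5 | 0.7 | −11% | +1% | −9% | −6% |
| 1 | 0.5 | −22% | +1% | −20% | −18% |

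A separate simulation run gave −7% where the table has −6% for the full change at 0.5 SD and correlation 0.5.

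**Step 5. Error rate.** With d measured in within-participant SD (0, 0.5 and 1.0), the unbalanced and unadjusted test rejected a true null in 0.016 to 0.019 of trials, against a nominal 0.0167. Near-balance without model terms rejected in only 0.0055 at 1.0, because position variance stays in the error term.

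**Step 6. Feasibility within gender.** One block of all six sequences puts each intervention at each site twice. One 3×3 Latin square adds one to each. A tenth row makes some cells 4 instead of 3. Over 2,000 lists built this way, Experimental and Control never differed by more than 1 at any site within a gender. When the two tenth rows are different rows of one square, the same held overall.

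**The case against.** The strongest reply is that the plan is silent, not wrong. It says sites and order are random and gives no method, so a balanced list may exist. This stands: a reader might infer that the plan prescribes unrestricted randomisation, but no sentence does so, and the 34% and 13% hold only if simple randomisation is used.

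The reply also has force on size. The documents give no position or order effect and do not describe a middle site. At 0.25 SD the full change gains about 1%, and at zero it loses up to about 1%. Adding both terms to an unbalanced allocation makes intervals 4% to 6% wider when effects are that small. It is therefore wrong to suppose that model terms alone always help.

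Two further readings are tempting and are not supported. A reader might infer biased contrasts or a false-positive problem. Random assignment keeps the contrasts unbiased on average, and the simulated error rate was close to nominal. A reader might also infer that gender stratification prevents balance and should be dropped. Exact balance is impossible with 10, which is not a multiple of 3, but it is equally impossible with 20, and near-balance fits inside each gender.

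Finally, the change takes more than naming two extra factors. Position and order vary within a participant and are not crossed with intervention, so they do not fit a wide-format repeated measures ANOVA. This is right, and the fix allows for it.

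**Conclusion.** The point holds as one of precision. The plan describes no balancing of site position or application order and no model term for either, while the one factor it stratifies on cancels in the main contrasts. For an assumed middle-site effect, correcting both parts narrows the Experimental–Control interval by about 1% at 0.25 SD (correlation 0.5), 6% to 7% at 0.5 SD (0.5), 11% at 0.5 SD (0.7) and 22% at 1 SD (0.5). If neither effect exists, the cost is about 1% or less. The effect sizes and correlations are assumptions, and the comparator is simple randomisation. Both parts are needed for the full gain: balance alone leaves the interval no narrower. The change is worth making because it is inexpensive and needs no more participants, not because the planned test is invalid.

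**What to change.** **Section 2.** Keep the gender strata and describe the list. Within each gender of 10, use one block of all six site-by-intervention sequences, one 3×3 Latin square and one further row, in random order. Take the two further rows as different rows of the same Latin square. Build the application-order list in the same way.

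**Section 5.2.** Record site and order with every test. Reconcile the mandibular description in Section 2 with the maxillary one here before positions are labelled.

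**Section 6.** State that intervention is a within-participant factor. Add site position and application order as fixed factors in a long-format or mixed model with participant as a random effect. Include a further random effect for site within participant, so that the five tests at one site are not treated as independent. Rewrite the sphericity provision to match.

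**If allocation is already complete without balance.** Pre-specify position alone. Under the same assumptions this narrows the interval by about 4% to 20% at 0.5 to 1 SD, and widens it by about 1% at 0.25 SD (correlation 0.5) and 3% at zero.

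**Cost.** A new allocation list, two more recorded items per test, a rewritten model paragraph and up to 4 of 38 error degrees of freedom. No extra participants or tests are needed.

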3.1 Experimental Equipment

3.1.1 Water Laser Device

Device: Er,Cr:YSGG Waterlase (Model MDX300), manufacturer: BOOLASE (USA), registration number: National Medical Device Approval 20153241177. The laser wavelength is 2780 nm and is suitable for various dental procedures. Two modes are predefined:

- Mode 1a (active laser): Power 1.0 W, water 15%, air 35%, frequency 30 Hz, H mode (soft tissue mode);
- Mode 1b (placebo laser): Power 0.1 W, other parameters same as Mode 1a.

All personnel must wear laser protective glasses during operation. The handpiece must be moved continuously to avoid localized heat accumulation.

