3.1.2 Electrocardiogram (ECG) Monitor

Device: Baolaite M7000 Multi-parameter Monitor (Guangdong Medical Device Approval 2012 No. 2210328), used for continuous monitoring of heart rate, blood pressure, and oxygen saturation. The cuff is placed on the upper arm, and the oxygen sensor is attached to the index finger. Data will be recorded throughout the procedure.

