3.2 Experimental Drugs and Materials

- Topical anesthetic: 2% lidocaine gel (Gandermal, Registration No.: H20150426);
- Placebo: Petroleum jelly;
- Other materials: 27G injection needle (Fukada), periodontal probe (Hu-Friedy), mouth prop (Ivoclar), dental mirror, sterile cotton swabs, timer, etc.

4. Outcome Measures

Primary outcome measures include:

- Penetration depth and VAS score at the moment of "sensation of foreign body";
- Penetration depth and VAS score at the moment of "pain";
- Heart rate at each needle insertion and the increase in heart rate (heart rate at pain moment – baseline heart rate).
- Penetration depth is calculated based on the exposed length of the needle (penetration depth = 30 mm – length outside the mucosa).

5. Study Procedure

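### No adverse-reaction check is planned before the first puncture, so both planned readings mix any laser reaction with the effects of needling

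*Combined protocol and SAP*

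**What the plan says.** Section 5.2 (Experimental Procedure) lists four steps: choose three sites; apply the interventions in random order; test; assess reactions. On testing it says: "Penetration tests will be performed at 10, 20, 30, 40, and 50 minutes after treatment". Each test records depth, VAS score and heart rate at first sensation and again at pain, so the needle is advanced until pain is reported. The last step reads: "Adverse reactions (redness, pain, bruising, etc.) will be assessed immediately after the procedure and at 24-hour follow-up".

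Four other places bear on this:

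- Section 2 gives each participant one Experimental site (1.0 W, then lidocaine gel), one Control site (0.1 W, then the same gel) and one Blank site (0.1 W, then petroleum jelly).
- Section 4 makes depth at pain a primary outcome, calculated as "penetration depth = 30 mm – length outside the mucosa".
- Section 3.1.1 recognises a thermal hazard: "The handpiece must be moved continuously to avoid localized heat accumulation".
- Section 3.1.2 says of the monitor: "Data will be recorded throughout the procedure". Section 4 requires heart rate at each needle insertion.

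The plan does not define the procedure, does not say whether reactions are recorded by site or by participant, gives no grading, and has no analysis of adverse reactions.

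**The concern.** The three reactions named in Section 5.2 (redness, pain and bruising) are also what repeated needling could plausibly cause. If the first look at the mucosa comes after the fifth puncture, a reaction at the Experimental site may come from the laser, the needle or both.

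The needle contribution need not be equal across sites. Each insertion stops at pain, so a site with better anaesthesia is entered more deeply. The result that would count as success for the laser is therefore also the one under which needle trauma may be greater at the laser site. In the other direction, mild redness from the laser could be hidden by needle redness at all three sites.

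At stake is whether the trial yields any needle-free observation of a hazard it already recognises. The primary efficacy outcomes are not affected.

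**Working it through.** **Which events precede the first assessment?** The answer depends on what *procedure* means.

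- *Whole session.* Section 5.2 carries the word in its heading and contains the penetration tests, and the reaction step is listed after them. Section 3.1.2 has the monitor recording throughout the procedure, and Section 4 needs heart rate at each insertion, so the procedure in that sense includes the insertions. All punctures then come first.
- *One site at a time.* Each site still receives its five punctures before its own first assessment.
- *Irradiation and application only.* The immediate assessment would then precede the punctures. Section 2 lends this some support, because it uses the plural of the word just after listing the interventions.

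The first reading is the natural one. The third is possible because the term is undefined.

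**Count on the natural reading.** Inputs: 3 sites (Sections 2 and 5.2), 5 tests (Section 5.2), 20 participants (Section 1).

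- Per participant: 3 × 5 = 15 insertions.
- In the trial: 15 × 20 = 300 insertions, of which 5 × 20 = 100 are at active-laser sites.

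The plan states no reaction rate, depth, standard deviation or power, so it has no figure to reproduce. The next two steps are illustrations on assumed values.

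**Excess from depth alone, with no laser harm.** Assume a per-puncture bruising risk q at Control depth, risk proportional to depth, independent punctures, and Experimental insertions r times as deep. The risk per site is 1 − (1 − q)^5 at Control and 1 − (1 − qr)^5 at Experimental.

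| q | Control | Experimental, r = 1.25 | Experimental, r = 2 | Excess (points, before rounding) |
|---|---|---|---|---|
| 2% | 9.6% | 11.9% | 18.5% | 2 to 9 |
| 5% | 22.6% | 27.6% | 41.0% | 5 to 18 |
| 10% | 41.0% | 48.7% | 67.2% | 8 to 26 |

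At r = 1 the excess is zero in every row.

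**Masking, with equal depth.** Assume a true laser reaction rate of 20% and an independent needle background b at both sites. The visible difference is 0.20 × (1 − b).

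- b = 0: 20 points
- b = 20%: 0.20 × 0.80 = 16 points
- b = 50%: 0.20 × 0.50 = 10 points
- b = 80%: 0.20 × 0.20 = 4 points

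Exact McNemar power with 20 pairs (two-sided 0.05, sites independent) is 0.20, 0.11, 0.05 and 0.02 respectively.

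**What a pre-puncture look would give.** Needle trauma at that look is zero. If 0 of 20 active sites react, the one-sided 95% upper limit is 1 − 0.05^(1/20) = 13.9%. The chance of seeing at least one reaction is 1 − 0.90^20 = 0.88 if the true rate is 10%, and 1 − 0.80^20 = 0.99 if it is 20%.

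**The case against.** A reader might infer that laser harm cannot be separated from needle trauma at all. The documents do not support that. The Control site receives the same gel and the same five tests, so a paired comparison by site removes the needle trauma the two sites share. What is left is any trauma due to a depth difference. Depth is recorded at every test, although it is measured after treatment, so adjusting for it is an imperfect remedy.

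Other parts of the case against also stand:

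- No document shows that redness, pain or bruising rises with depth. Surface redness from equal numbers of punctures could be the same at all sites, and the excesses tabulated above come from assumed inputs.
- A reader might infer that reactions are recorded per participant and so cannot be assigned to an intervention. The plan is silent on this, and silence does not establish it.
- Section 4 names no safety outcome and Section 6 plans no adverse-reaction analysis, so no planned safety conclusion is biased. With 20 participants a formal comparison is weak in any case: power is 0.20 for a 20% laser reaction rate even with no needle background.
- An early look misses delayed laser reactions, so it cannot carry a safety statement alone.

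None of this supplies a needle-free reading. On the natural reading the plan has none, and assessing laser and needling only in combination leaves the recognised heat hazard without an observation of its own.

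**Conclusion.** The point holds in a limited form. On the natural reading of Section 5.2, no check falls between irradiation and the 10-minute puncture, and both planned assessments follow five insertions to pain at each site. Redness, pain and bruising would then mix laser effect with needling. A paired comparison by site would cancel the shared part but not any part due to deeper insertion, and it depends on site-level recording that the plan does not state.

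The count of 300 insertions before the first assessment is firm if the procedure means the whole session. The extent of the mixing is not known: the 2 to 26 point range illustrates what assumed risks and depth ratios would produce and is not an estimate for this trial. This is an inexpensive improvement to the safety record, and it leaves the efficacy comparison as it is.

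**What to change.** In Section 5.2:

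- Add a brief visual inspection of each site after irradiation and gel or jelly application and before the 10-minute test, recorded by site.
- State that the procedure ends after the 50-minute test.
- Record the end-of-session and 24-hour assessments by site as well.
- Report the pre-puncture record as the needle-free reading of immediate laser reactions. Report the later readings alongside it as laser plus needling, since delayed laser reactions appear only there.

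The cost is a few seconds per site for the existing operator or assistant and three extra rows on the form. No intervention or test time changes. There are two downsides: slight extra handling within the 10-minute window, and an inspection that may be made by an unblinded operator, since Section 2 states blinding for participants only. Keeping the check visual also avoids asking participants to compare sensations between sites, which could draw attention to the difference between 1.0 W and 0.1 W.

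### Single-step Bonferroni is valid, but over three intervention pairs it gives up power on the laser contrast that a step-down test would keep at the same 5% familywise error

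*Combined protocol and SAP*

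**What the plan says.** Section 2 (Group Allocation) has three sites in each participant "randomly assigned to one of the following three interventions": active laser then lidocaine gel (Experimental), placebo laser then lidocaine gel (Control), and placebo laser then petroleum jelly (Blank). Section 1 plans the study "with a total of 20 participants (10 males and 10 females"), so each intervention contrast is a within-participant comparison on at most 20 pairs.

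Section 5.2 adds five measurement times: "Penetration tests will be performed at 10, 20, 30, 40, and 50 minutes after treatment". Section 6 then sets out the analysis: "Repeated measures ANOVA will be used to compare differences across time points and groups", followed by "Pairwise comparisons will be performed using Bonferroni correction with significance level" 0.05, and "A p-value < 0.05 will be considered statistically significant".

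Section 6 does not say how many comparisons the correction covers, whether they are made on the average over time or at each time, or whether any contrast ranks first. It mentions no step-down or gated rule. No effect size, standard deviation or power is given anywhere.

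**The concern.** Three interventions give three pairs. Single-step Bonferroni tests each pair at 0.05/3, whatever the other two show. With three means that is stricter than 5% familywise control requires, because the three equalities are logically linked: if one is false, at most one of the other two can be true.

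Experimental versus Control is the only pair in which the gel is held constant and only the laser power differs, so it bears most directly on the question in the official title. With 20 participants, an avoidable loss of power on that pair raises the risk of missing a real laser effect.

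**Working it through.** **Inputs from the document.** Three interventions per participant (Section 2); 20 participants (Section 1); Bonferroni and 0.05 (Section 6).

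**Assumptions.** The family is the three intervention pairs within one outcome. Tests are two-sided paired t-tests with 19 degrees of freedom. The effect d is the mean Experimental-minus-Control difference divided by the SD of that paired difference, taken from 0.2 to 1.2. The plan has no power figure of its own to reproduce.

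**Step 1: the level.** 0.05/3 = 0.0167. The critical |t| on 19 df is 2.093 at 0.05 and 2.625 at 0.0167.

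**Step 2: why a step-down keeps 5%.** The rule (Shaffer) compares the smallest p with 0.05/3; if it passes, the other two are each compared with 0.05. The number of true equalities among three means can only be three, one or none.
- Three true: any false rejection needs the smallest p to be at or below 0.05/3, which has probability at most 3 × 0.05/3 = 0.05.
- One true: rejecting it needs its own p to be at or below 0.05, which has probability at most 0.05.
- None true: no false rejection is possible.

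Anything Bonferroni rejects has p at or below 0.05/3, so the first step is passed and the rule rejects it too.

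**Step 3: simulated familywise error of the step-down** (20 participants, equicorrelated arms, paired SD 1): 4.7% with all arms equal; 4.3% and 4.9% with Experimental = Control and Blank 0.5 or 1 SD away; 5.1% with Control = Blank. That is 5% or less, within simulation error.

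**Step 4: the cost of 0.0167 against 0.05.** Power = P(|T| > critical value), where T is noncentral t with 19 df and noncentrality d√20. For d = 0.66 the noncentrality is 0.66 × 4.472 = 2.95.

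| d | Power at 0.05 | Power at 0.0167 | Loss (points) |
|---|---|---|---|
| 0.20 | 13.6% | 5.9% | 7.7 |
| 0.40 | 39.7% | 23.0% | 16.7 |
| 0.50 | 56.5% | 37.3% | 19.2 |
| 0.66 | 79.9% | 63.1% | 16.9 |
| 0.80 | 92.4% | 81.8% | 10.6 |
| 1.00 | 98.9% | 95.8% | 3.0 |
| 1.20 | 99.9% | 99.5% | 0.5 |

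The loss peaks at about 19 points near d = 0.50 to 0.55 and nearly vanishes for large effects. To match the 0.05-level power of 20 participants, Bonferroni would need 27 at d = 0.66 or 30 at d = 0.50.

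**Step 5: how much the step-down recovers.** The laser contrast reaches the 0.05 level only after the smallest p has passed 0.0167. Simulated power for Experimental versus Control at d = 0.66:

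| Control minus Blank | Bonferroni | Holm | Shaffer |
|---|---|---|---|
| 0 | 63% | 67% | 72% |
| 0.5 SD | 63% | 75% | 80% |
| 1.0 SD | 63% | 80% | 80% |

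**Step 6: if groups are compared at each time.** Three pairs × five times = 15 tests, and 0.05/15 = 0.0033. The three-arm shortcut does not apply directly to one family of 15, but it does apply within each time if each is allotted 0.05/5 = 0.01 (0.0033 for the smallest p, then 0.01). At d = 0.66, power per time is 38% under Bonferroni over 15. Under the step-down it is 54% to 55% if Control exceeds Blank by 0.5 to 1 SD, and 44% if they are equal.

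**The case against.** The strongest reply is that nothing here is wrong. Bonferroni is conventional and controls familywise error, so preferring a step-down is a choice about efficiency. That stands.

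A reader might infer that the plan loses 17 points of power on its key contrast for nothing. The document does not support that reading, for four reasons.

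- **The 17 points is not a property of this plan.** It holds at d = 0.66, an assumed effect chosen because it gives about 80% power at 0.05 with 20 pairs.
- **The gain is conditional.** It is nearly complete only if Control clearly differs from Blank. A lidocaine gel may well outperform petroleum jelly, but the document states no expected difference.
- **The family and the key contrast are inferred.** No contrast is ranked first. Comparisons averaged over time (3), between interventions at each time (15) or between times (10) all fit the wording of Section 6.
- **The step-down has a price.** It has no simple matching simultaneous confidence intervals. If laser and control are truly equal and Blank clearly differs, the false-positive rate of the laser contrast rises from about 1.7% to about 5%. The ceiling is the same, but the plan uses less of it.

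The last point matters more because Section 4 lists several primary measures and no adjustment across them is stated. Suppose, for illustration, six independent outcomes with laser equal to control and Blank clearly different. The chance of at least one false laser claim is 1 − (1 − 0.0167)^6 = 9.6% under Bonferroni and 1 − 0.95^6 = 26.5% under the step-down. Correlation between outcomes would lower both. This trade-off should be stated, but multiplicity across outcomes needs its own rule, and an over-strict test within each outcome is a poor substitute for one.

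**Conclusion.** The point holds as an inexpensive improvement. Single-step Bonferroni is valid as planned. If the family is the three intervention pairs, a three-arm step-down offers the same 5% familywise control within an outcome and is never less powerful.

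The size depends on an effect the document does not give. Across d = 0.2 to 1.2 the loss at 0.0167 is about 0.5 to 19 points, and it exceeds 10 points from about d = 0.3 to 0.8. The logic in Step 2 is certain; the sizes rest on 20 complete pairs and the paired t model.

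**What to change.** In Section 6:

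1. State the family. For each outcome it is the three intervention comparisons from the repeated measures model, taken on the group effect averaged over the five times. If groups are also compared at each time, say so, and apply the rule within each time at whatever level that time is allotted.
2. State the rule. Compare the smallest of the three unadjusted p-values with 0.05/3. If it is significant, compare each of the other two with 0.05 (Shaffer); otherwise stop. Holm (0.05/3, 0.05/2, 0.05) is a simpler alternative with a smaller gain.
3. State the limits. Show Bonferroni intervals beside the tests, since the step-down has no simple matching simultaneous intervals. Note that the false-positive rate of the laser contrast itself can rise from about 1.7% to at most 5%, and that the 5% applies within one outcome only while the primary outcomes remain unadjusted.

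The cost is a few lines of text, fixed before analysis, and ordering three unadjusted (LSD) p-values from SPSS by hand. No extra participants, visits or data are needed.
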